Positron emission tomography examination of the brain using [¹¹C]osimertinib (administered before the start of PET) will be carried out 3 times: the first time at baseline (PET1; Visit 2 [Day 1]), the second time after the first oral dose of osimertinib of 80 mg (PET2; Visit 3 [Day 2], or within 1 week after baseline) and the third time after 3 weeks treatment with 80 mg oral dose osimertinib daily (PET3; Visit 5 [Day 29]) (Figure 1B).

At each PET examination [¹¹C]osimertinib will be given IV as a microdose (<10 µg), at a radioactivity of 300 MBq/70 kg of body weight. The minimum injected radioactivity will be 200 MBq/70 kg of body weight and the maximum injected radioactivity will be 330 MBq/70 kg of body weight. Brain radioactivity will be measured for 90 minutes (minimum 60 minutes) in the PET examination system (high resolution research tomograph [HRRT]).

The PET2 examination and the PET3 examination will be performed on Visit 3 and Visit 5 after IV [¹¹C]osimertinib administration. The IV dose will be given ~6 hours after the oral osimertinib 80 mg to coincide with the median time of maximum drug concentration (T_{max}) of the oral dose. All participants will receive at least 3 weeks (21 days) treatment with 80 mg oral dose of osimertinib once daily between the PET2 examination and PET3 examination visits.

[figure not shown]
On completion of the imaging phase (ie, at the PET3 examination), patients may continue to take osimertinib tablets (80 mg once daily) as a single agent in the CAP depending on agreement between the patient and the Investigator. This will continue until, in the opinion of the Investigator, the patients are no longer deriving clinical benefit, or the patients stop taking osimertinib for any other reason. No clinical data will be collected during this phase other than sudden death of unknown reason, SAEs that may or may not be related to osimertinib, outcomes of pregnancy and IP dispensing/accountability (Figure 1).

Dose reduction of osimertinib (to 40 mg once daily) according to clinical practise will be allowed in the CAP if deemed necessary by the Investigator due to AEs.

[figure not shown]

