j Required at baseline. Repeated during the imaging phase only if clinically indicated at any time point or subsequently at follow-up 30 (± 7) days after last administration of study medication (for example to follow up on a cardiac AE).

k Patient must weigh at least 40.0 kg and no more than 100.0 kg (see Section 3.1).

l Blood and urine samples will be collected for routine laboratory testing (haematology, clinical chemistry), and urine analysis (see Section 5.4).

m Serum pregnancy test at screening and follow-up. FSH and LH to be tested at screening. All other visits, urine pregnancy test.

n Current medications will be reviewed and recorded.

o PK sampling: at pre-administration, 2, 4 and 7.5 hour(s) (can be modified if necessary). During PET examinations, PK sampling schedule maybe limited to the PET examination time (see Section 5.3.2.2).

p CSF samples will be collected at pre-administration prior to start of treatment and at the PET3 examination day.

q A re-biopsy from tissue may be collected as part of clinical routine upon disease progression during continued access treatment. A blood sample (2 x 10 mL) will be collected at screening only for additional option for central confirmation of EGFR status if tissue confirmation is not possible.

r An arterial line will be inserted on the day the patient arrives for the administration of the IP and PET examination. The arterial line will be placed in the opposite arm than the 1 being used to administer the single IV microdose of [¹¹C]osimertinib bolus injection. A venous access line will also be inserted to collect blood samples. The arterial line will be removed at the conclusion of the PET examinations, after the last sample has been collected. The placement of the arterial line, venous access line, administration of the IV microdose [¹¹C]osimertinib bolus injection, PET examinations (see Section 5.3.2.2), and removal of the arterial line (and venous access line) will take place on the same day. Standard institutional procedures will be followed for arterial line removal. In case of failure with arterial sampling during the PET examination, because of spasm or blood clots, the PET examination will continue and venous samples will be taken according to the planned schedule of arterial samples.

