5.4 Pharmacokinetics

5.4.1 Collection of PK samples

Venous blood sampling for osimertinib PK: venous samples will be collected at selected time points to determine the PK of osimertinib and its metabolite, AZ5104 after single administration and at steady state.

Although every attempt should be made to collect all samples as per the CSP-defined time points, it is accepted that this will not always be possible and therefore it is essential that the actual time and date of collection of each blood sample (whether collected as per CSP or not) is recorded in the pCRF. See Section 5.8 for volume of samples to be collected.

Samples will be collected, labelled, stored, and shipped as detailed in the Laboratory Manual.

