7.2 Dose and treatment regimens

Radioligand [¹¹C]osimertinib will be administered IV, synchronized with the start of the PET system examination. Each patient will undergo a single administration of [¹¹C]osimertinib repeated 3 times over the study (Day 1, Day 2 [or up to Day 8] and Day 29). Mass injected will not exceed 10 µg per injection. Radioactivity injected will be 300 MBq/70 kg of body weight. The minimum injected radioactivity will be 200 MBq/70 kg body weight and the maximum radioactivity injected will be 330 MBq/70 kg body weight.

The first administration of [¹¹C]osimertinib will be administered on Day 1 in the clinic via an IV route. After 90 minutes of the PET examination, the patient may be discharged from the clinic.

The second administration of [¹¹C]osimertinib will be approximately 6 hours after the single oral 80 mg administration of osimertinib to coincide with the oral T_{max}. The oral administration can be with or without food. Pharmacokinetic samples will be collected (up to 6 hours) and the PET examination will be conducted for 90 minutes (minimum 60 minutes) after the IV administration is given. This visit can happen on Day 2 (1 day after the first IV administration) and up to Day 8.

Osimertinib 80 mg once a day will be taken by the patient from the day of the second PET examination for at least 21 days before the PET3 examination will be scheduled. On Day 14 (±2 days), a clinical visit to evaluate the safety of the patient will be performed.

Patients will come to the clinic on Day 29 (±3 days), prior to taking their daily dose of osimertinib. It is important to record date/time of the last administration taken before the visit and make sure that the trough (pre-administration) sample is collected no less than 18 hours and no more than 30 hours after the last administration before the PK blood sample. On Day 29, in addition to receiving their daily administration of osimertinib, patients will receive [¹¹C]osimertinib via IV route at approximately 6 hours after the oral administration. Safety information will be collected during this visit and the patient will be discharged after the PET examination is finished. Computed tomography/MRI measurement can be conducted on the same day or within 7 days of this visit.

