3.2 PK Variables

All PK concentrations will be listed. Average of the concentrations between the PET measurement will also be summarised. Summary data for patients in the PK analysis set will be presented in the table. The following PK parameters will be summarized for patients in the PK analysis set. There will be no PK parameters presented for patients after the first dose (PET2 day) and only steady state PK parameters (PET3) will be calculated.

Pharmacokinetic parameters for an individual patient were not included in the summaries if the patient missed a single dose within 3 days of the planned PK sampling, received a different dose on the PK sampling day or ≥ 7 days of dosing were missed with <10 days back on daily administration before the PK sampling day. This list of patients was provided by the pharmacokineticist. The pre-dose time point on PET3 was also used as the 24 hr time point to calculate the AUC_{ss} since at the time of PET3, if the patient met the above criteria, osimertinib and AZ5104 are expected to be at steady state.

Osimertinib: Area under the concentration time curve from 0-24 hrs at steady state (AUC_{ss}), maximum plasma concentration at steady state (C_{ssmax}), time of maximum plasma concentration at steady state (T_{ssmax}), apparent clearance at steady state (CL_{ss}/F).

AZ5104: AUC_{ss}, C_{ssmax}, T_{ssmax}, AZ5104 AUC_{ss}/osimertinib AUC_{ss}, AZ5104 C_{ssmax}/osimertinib C_{ssmax}.

For PET2, ie, after single dose of osimertinib, no PK parameters will be presented due to planned limited sampling and only the concentration data will be listed and summarized.

Events or changes to procedures that may impact the evaluation of PK data including, but not limited to, vomiting following oral dosing occurring within the timeframe of 2 times the median t_{max}, wrong dose administered, patient received a prohibited concomitant medication,

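### The oral PK sampling schedule is inconsistent across three places, the listed times omit the 6 h point the scans are built around, and the SAP's PET-window average has no defined samples

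*Protocol*

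**What the plan says.** **Sampling times.** Protocol Table 1 schedules oral PK blood at PET2 and PET3. Footnote o gives the times: "PK sampling: at pre-administration, 2, 4 and 7.5 hour(s) (can be modified if necessary". It adds: "During PET examinations, PK sampling schedule maybe limited to the PET examination time". It refers to Section 5.3.2.2, which describes only the blood sampling for [11C] radioactivity and radiometabolites.

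**Number of samples.** Protocol 5.8, Table 3, counts 10 osimertinib PK samples per patient, written as five times two, at 2 mL each, 20 mL in all.

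**End of sampling.** Protocol 7.2, in the paragraph on the second tracer administration (PET2), says: "Pharmacokinetic samples will be collected (up to 6 hours". The Day 29 paragraph (PET3) sets no such limit.

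**Scan timing.** Protocol 1.4: "The IV dose will be given ~6 hours after the oral osimertinib 80 mg to coincide with the median time of maximum drug concentration". The same section says: "Brain radioactivity will be measured for 90 minutes (minimum 60 minutes) in the PET examination system".

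**What the SAP does with the samples.** SAP 3.2: "Average of the concentrations between the PET measurement will also be summarised". It names no samples and gives no formula. On derived parameters, "only steady state PK parameters (PET3) will be calculated"; for PET2, concentrations are only listed and summarised. T_ssmax is one of the secondary outcome variables (Protocol 2.2, SAP 1.1).

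**Actual times.** Protocol 5.4.1 requires that the "actual time and date of collection of each blood sample (whether collected as per CSP or not) is recorded in the pCRF".

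**The concern.** The three protocol texts give the site different instructions: four draws or five per visit, and a last draw at PET2 at 7.5 h or no later than 6 h.

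The time missing from the explicit list is also the one the design targets. The scans are placed at about 6 h so that they coincide with the oral peak, and without a sample near 6 h there is no direct evidence that a patient was at peak when the tracer went in. T_ssmax is read from the same few times. At PET2 no PK parameters are derived, so the plasma concentrations are the only osimertinib PK result for that visit. The planned average is also open to more than one calculation, so two analysts could report different figures from the same data.

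**Working it through.** **1. Reproducing the plan's sample count.**
- Footnote o: 4 times × 2 visits = 8 samples; 8 × 2 mL = 16 mL.
- Table 3: 5 × 2 = 10 samples; 10 × 2 mL = 20 mL.
- The listed times do not reproduce Table 3. They fall short by one tube per visit.
- Adding a 6 h sample gives pre-dose, 2, 4, 6 and 7.5 h: 5 × 2 = 10 samples, 20 mL, which matches Table 3 exactly.

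**2. Samples inside the scan.** The window opens at about 6 h. It closes at 6 + 1.5 = 7.5 h, or at 6 + 1 = 7 h if only the minimum is acquired.

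| Schedule | In 6–7.5 h | In 6–7 h |
|---|---|---|
| Footnote o as listed | one (7.5 h, at the closing edge) | none |
| Footnote o plus 6 h | two (6 and 7.5 h) | one (6 h) |

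The venous draws at 30, 60 and 90 minutes after injection are listed for [11C] radioactivity and metabolites, so they are not counted as oral PK samples.

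**3. What T_ssmax can read.** An observed Tmax must fall on a sampling time. On the listed times the nominal values are 0, 2, 4 and 7.5 h (or 24 h, if the pre-dose value reused as the 24 h point were the highest). Six hours is not among them.

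**4. How much this moves the numbers.** The documents give no half-life, so this step is an illustration on assumptions: one compartment, oral dosing every 24 h at steady state, true peak at 6 h, half-life 12 to 72 h. The profile is

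C(t) ∝ exp(−ke·t)/(1 − exp(−24·ke)) − exp(−ka·t)/(1 − exp(−24·ka)),

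with ke = ln 2 / half-life and ka solved so that the maximum is at 6 h.

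| Half-life (h) | ka (per h) | C(4)/C(6) | C(7.5)/C(6) | C(7.5) / mean over 6–7.5 h | Mean of C(4) and C(7.5) / mean over 6–7.5 h |
|---|---|---|---|---|---|
| 12 | 0.262 | 96.2% | 98.5% | 99.0% | 97.9% |
| 24 | 0.308 | 97.8% | 99.2% | 99.4% | 98.7% |
| 48 | 0.333 | 98.8% | 99.5% | 99.7% | 99.3% |
| 72 | 0.341 | 99.2% | 99.7% | 99.8% | 99.5% |

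- In every row the 7.5 h value exceeds the 4 h value, so a true 6 h peak reads as 7.5 h: 7.5 − 6 = 1.5 h late, and 1.5/6 = 25%.
- Observed C_ssmax is 98.5% to 99.7% of the true peak.
- Two natural readings of the undefined average, the single 7.5 h value or the mean of the bracketing 4 h and 7.5 h values, both lie within about 2% of the true window mean.
- The trapezoidal AUC over 24 h on the listed times is 99.3% to 99.6% of the true value.

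**The case against.** The protocol is more flexible than the bare list. The times may be modified, PK sampling may be confined to the scan period, and every actual time is recorded. Table 3's fifth tube, read with the 6 h limit in 7.2, may mean that a 6 h draw was already intended, and the Laboratory Manual, which is not among the documents, may state it. Table 3 is thin evidence taken alone, since another of its rows does not multiply out (1.8 × 3 is 5.4, shown as 5.2). Six hours is a median, so individual peaks will scatter around it, and any sampling grid limits Tmax to its own points. The outcome is qualified as depending on what the data allow. The listed primary outcomes come from radioactivity measurements, so none of them uses the oral plasma concentration. The study is descriptive.

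Most of this stands, and it rules out several stronger readings that a reader might infer:
- **The average cannot be computed.** It can: the samples on either side of injection could be averaged, or the times changed. It is undefined, not impossible.
- **T_ssmax can never be right.** Modified or actual times can differ from the list. With an even number of patients the median could also fall midway between 4 and 7.5 h, at (4 + 7.5)/2 = 5.75 h. The limit applies to individual values on the nominal times.
- **A 6 h peak could equally read 4 h.** The illustration gives 7.5 h at every half-life tried.
- **Section 7.2 leaves PET3 without a sample after injection.** The 6 h limit is in the PET2 paragraph only, and it permits a draw at 6 h itself.

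The flexibility does not resolve the inconsistency, however. The permission to modify names no replacement time and no trigger. Confining sampling to the scan would drop the earlier draws that T_ssmax and AUCss need. Recording actual times documents a draw but does not place one at 6 h.

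**Conclusion.** The point holds as an inconsistency to reconcile and an undefined summary, with a modest consequence. Footnote o, Table 3 and the PET2 paragraph of 7.2 cannot all be followed. If the listed times are followed, nothing is drawn at the time the scans target and an individual T_ssmax of 6 h is unobservable at PET3. At most one listed sample falls in the scan, and none if it lasts 60 minutes.

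The numerical loss is small for C_ssmax and for the scan-time concentration: about 2% or less, given the assumed one-compartment shape, a peak at 6 h and a half-life of 12 to 72 h. The real losses are the resolution of T_ssmax (a 6 h peak read 1.5 h late), direct confirmation that the scan was at peak, and reproducibility of the average. The primary imaging results are not called into question.

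**What to change.** 1. **Table 1, footnote o:** assign the fifth tube counted in Table 3 to 6 h, drawn just before the IV tracer injection, at PET2 and PET3. The schedule becomes pre-dose, 2, 4, 6 and 7.5 h.
2. **Protocol 7.2:** reconcile the end of PK sampling at PET2 with footnote o, so that both give the same last time.
3. **SAP 3.2:** define the PET average as the time-weighted mean of the 6 h sample and the end-of-scan sample, using actual times. If the scan is shortened, draw the last sample at its actual end; otherwise a 60-minute scan would still contain only one. State that T_ssmax is resolved only to the sampling times.

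**Cost:** a short edit in each of three places and one more timed draw per PET visit than footnote o lists. The total is 10 samples and 20 mL, as Table 3 already budgets, through a venous line already placed on PET days, with no extra visit.

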4.1 Screening/Enrolment period

Screening procedures will be performed according to the Study Plan for the imaging phase (Table 1). At screening, consenting patients are assessed to ensure that they meet eligibility criteria (Sections 3.1 and Section 3.2). Patients who do not meet these criteria must not be enrolled in the study.

Patients will be considered to be in the screening period until all Visit 1 assessments are completed and eligibility is confirmed. Patients will be considered to be in the treatment period after the first PET examination with [¹¹C]osimertinib.

The following assessments and procedures should be performed within 28 days prior to the first administration of the IP:

- Signed informed consent for the study and pharmacogenetics informed consent (optional).
- Review inclusion/exclusion criteria; ensure that patient has documented an EGFRm (local testing conducted at an accredited laboratory) known to be associated with EGFR-TKI sensitivity (eg, G719X, exon 19 deletion, L858R, L861Q) and a T790M mutation in EGFR if previously treated with EGFR-TKI.
- Demographics (sex, age, self-reported race/ethnicity).
- Medical/surgical history including smoking status.
- Prior and concomitant medications including prescribed and over-the-counter preparations and previous cancer therapies (if applicable), check against exclusion criteria, restrictions (see Section 7.7) and Appendix B.
- Physical examination, WHO performance status, vital signs (supine BP and pulse, body temperature), ECG, echocardiogram (ECHO) or multiple gated acquisition scan (MUGA) for left ventricular ejection fraction (LVEF), body weight and height
- Haematology, clinical chemistry and coagulation, serology (hepatitis B and hepatitis C status) and urine analysis.
- Serum or urine pregnancy test (pre-menopausal women of childbearing potential).
- Ophthalmology: Full ophthalmic assessment, including slit lamp examination, should be performed at screening and if a patient experiences any visual symptoms (including blurring of vision), with additional tests if clinically indicated. Ophthalmology examination results should be collected in the pCRF. Any clinically significant findings, including those confirmed by the ophthalmologist must be reported as an AE. Photographs should be performed to record any clinically significant findings. These photographs should be available for central review by AstraZeneca and AstraZeneca representatives if necessary. Patients experiencing corneal ulceration will not be permitted to restart the IP.
- AEs

4.2 Treatment period

Descriptions of the procedures for this period are included in the Study Plan with exceptions of the following specific requirements for the treatment period.

4.2.1 Sequence of assessments

It is important that arterial and venous sampling occurs as close as possible to the scheduled time. In order to achieve this, other assessments scheduled at the same time may be initiated prior to the time point. The sequence to be followed at a particular post-administration time point is:

1. ECGs
2. Vital signs
3. Blood sample (at scheduled time)
4. Any other measurements

Before the first administration of [¹¹C]osimertinib, pre-administration ECGs and vital signs should be collected within 60 minutes prior to administration. All Day -1 procedures in the imaging phase must be performed in the clinic on Day -1 or pre-administration on Day 1; patients may be admitted on Day 1 if the Day -1 activities (see Table 1) can be completed on the same day. If the patient has been screened within 48 hours of Day 1, safety laboratory tests (haematology, coagulation, clinical chemistry and urine analysis) do not need to be repeated.

4.3 Continued access phase (CAP)

During the CAP osimertinib can be taken with or without food. Following completion of the imaging phase, patients may continue to take osimertinib as a single agent, if they and the Investigator deem it appropriate, until such time as the Investigator believes they are no longer deriving clinical benefit or they stop taking osimertinib for any other reason. Patients will be seen as per their normal routine clinical schedule. No clinical data will be collected during this phase other than sudden death of unknown reason, SAEs that may be related to osimertinib, outcomes of pregnancy and IP dispensing/accountability.

4.4 Follow-up period

Descriptions of the procedures for this period are included in the Study Plan with exceptions of the following specific requirements for the follow-up period:

Those patients who do not proceed into CAP will return to the clinic for follow-up assessments 30 days (± 7 days) after their last administration in the imaging phase; follow-up assessments are detailed in Table 1.

If the patient's last administration of osimertinib is in the CAP (ie, after the imaging phase), the patient should be contacted 30 days after their last administration of osimertinib to follow up on any existing SAEs and monitor for new SAEs that may be related to IP.

A post-study assessment will be performed 7 working days after the last [¹¹C]osimertinib has been infused and the PET examination is completed. In the event of a holiday or weather delay the follow-up call may be postponed 1 to 2 working days. If the patient can not be contacted within 14 days as scheduled, the Investigator designee/centre staff must try again.

The patient will be asked about any symptoms or ill-effects since the time of the procedure. The patient will also be reminded to:

- Contact the Investigator or designee at the PET centre, if within the follow-up period following participation in the study, they feel ill effects related to the study.

The post study follow-up call and outcome will be recorded in the patient's medical record.

5. STUDY ASSESSMENTS

The In Form Web Based Data Capture (WBDC) system will be used for data collection and query handling. The Investigator will ensure that data are recorded on the pCRF as specified in the CSP and in accordance with the instructions provided.

The Investigator ensures the accuracy, completeness, and timeliness of the data recorded and of the provision of answers to data queries according to the Clinical Study Agreement (CSA). The Investigator will sign the completed pCRFs. A copy of the completed pCRFs will be archived at the study centre.

